3.6.2.2 Vaccination

Vaccination of subjects during treatment with CFZ533 and prior to clearance of the antibody is likely to result in therapeutic failure (i.e., non-protective antibody titers) due to the pharmacologic activity of the antibody. For subjects participating in this study, all vaccinations should be up to date based on local guidelines. Reduced or absent immunization effectiveness may be expected for both live (attenuated) and non-live (e.g. inactivated (killed), viral-vector, mRNA) vaccines. For further information refer to the Investigator's Brochure Section 4.2.7.

Administration of live (attenuated) SARS-CoV-2 vaccines is prohibited within 8 weeks of the first infusion of CFZ533, while receiving CFZ533 treatment and for at least 14 weeks after the last dose of the study medication.

While there is no absolute contraindication for the use of non-live (e.g. inactivated (killed), viral-vector, mRNA) SARS-CoV-2 vaccines, reduced or absent immunization effectiveness may be expected during treatment with CFZ533 and until 14 weeks after the last dose.

If treatment with CFZ533 is stopped, insufficient humoral immune response is likely to persist until 14 weeks after the last dose (until CFZ533 exposure decreases in the blood and tissues below the pharmacologically relevant level).

If SARS-CoV-2 vaccine is considered mandatory by local governance, administration of the vaccine should be provided at least 4 weeks before randomization or postponed for at least 14 weeks following the last dose of study drug, due to anticipated reduced or absent immunization effectiveness in treated patients.

Although there is no mandate to vaccinate clinical trial participants against SARS-CoV-2 prior to entry into the trial, patients will be advised to have completed vaccination series (if multi-dose regimen) against SARS-CoV-2 at least 4 weeks prior to randomization (or as long as needed before the first dose of CFZ533 based on when the protective immune response is expected to develop as indicated for the specific vaccine), if available, and according to local practice.

Patients who have decided not to get vaccinated may enter the trial if they have been informed that, should they receive a SARS-CoV-2 vaccination during the trial, the vaccination would likely be ineffective, and maximizing vaccine effectiveness would require study drug discontinuation and a waiting period of at least 14 weeks before vaccination.

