6.6 Permitted dose adjustments and interruptions of study treatment

Study drug dose adjustments and/or interruptions are not permitted in this study; in case of an AE or for any reason (e.g., non-compliance, operational hurdle) resulting in a deviation from the required dosing scheme, consultation and agreement with Novartis will be necessary to decide whether the subject can continue or needs to be withdrawn from the study. Any change in dosing must be recorded on the Dosage Administration Record eCRF. In case of notable adverse events, SAEs including loss of efficacy and/or associated PK/PD data collected during the study, changes to a different dosing scheme level may be considered and implemented via a protocol amendment.

Upon review data at interim analysis, dose adjustment for study drug may occur. This will be implemented via a protocol amendment.

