6.7 Emergency breaking of assigned treatment code

Emergency code breaks must only be undertaken when it is required to in order to treat the subject safely. Most often, study treatment discontinuation and knowledge of the possible treatment assignments are sufficient to treat a study subject who presents with an emergency condition. Emergency treatment code breaks are performed using the IRT. When the investigator contacts the system to break a treatment code for a subject, he/she must provide the

requested subject identifying information and confirm the necessity to break the treatment code for the subject. The investigator will then receive details of the investigational drug treatment for the specified subject and a fax or email confirming this information. The system will automatically inform the study monitor for the site and the Study Team that the code has been broken.

It is the investigator's responsibility to ensure that there is a dependable procedure in place to allow access to the IRT cards at any time in case of emergency. The investigator will need to provide:

- protocol number
- study drug name
- subject number.

In addition, the investigator must provide oral and written information to inform the subject how to contact his/her backup in cases of emergency when he/she is unavailable to ensure that un-blinding can be performed at any time.

An assessment will be done by the appropriate site personnel and sponsor after an emergency unblinding to assess whether or not study treatment should be discontinued for a given subject.

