If discontinuation of study treatment occurs, the investigator must determine the primary reason for the subject's premature discontinuation of study treatment and record this information on the Dosage Administration CRF. The investigator must also contact the IRT to register the subject's discontinuation from study treatment.

Patients who discontinue study treatment are to continue their study participation, and to complete all study visits.

Patients who decide they do not wish to participate in the study further should NOT be considered withdrawn from the study UNLESS they withdraw their consent. If they fail to return for the study visits for unknown reasons, every effort (e.g. telephone, e-mail, letter) should be made to contact the subject. This contact should preferably be done according to the study visit schedule.

The following data should be collected at minimum via telephone/email contact:

- new / concomitant treatments
- adverse events/Serious Adverse Events

Any unresolved AEs will be followed with additional post-study visits as determined appropriate by the study site investigator and sponsor.

Patients who discontinue the study must be reminded not to become pregnant for 14 weeks after the last dose of study medication.

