8.1 Assessment schedule

Subjects should be seen for all visits/assessments as outlined in the assessment schedule or as close to the designated day/time as possible.

Missed or rescheduled visits should not lead to automatic discontinuation. Subjects who prematurely discontinue the study drug for any reason should be continuing their study participation, i.e., to complete all study visits.

If an epidemic or pandemic (e.g. COVID-19 pandemic) limits or prevents on-site study visits, alternative methods of providing continuing care may be implemented. Phone calls, virtual contacts (e.g. teleconsult) or visits by site staff to the participant's home depending on local regulations and capabilities, can replace on-site study visits, for the duration of the pandemic until it is safe for the participant to visit the site again.

Table 8-1 Assessment schedule

Epoch	Screening		Treatment								Follow Up					
Visit Name	SCR	BL	Treatment								Follow Up				EOS	
Visit Numbers	1	2	101	102	103	104	105	106	199	201	202	203	204	205	206	299
Week	-4 to -1		1	3	5	9	13	17	21	25	29	33	37	41	45	49
Day	-28 to -8	-7 to -3	1	15 ±1	29 ±2	57 ±2	85 ±2	113 ±2	141 ±2	169 ±3	197 ±3	225 ±3	253 ±3	281 ±3	309 ±3	337 +3
Pre/Post ¹			Pre	Post	Pre	Post	Pre	Post	Pre	Post	Pre	Post	Pre	Post		
Informed consent	X															
Genetic consent	X															
Eligibility criteria	X	X														
Medical history/current conditions	X															
Demography	X															
Body height	X															
Body weight	X	X	X	X	X	X	X	X	X	X	X	X	X	X	X	X
Body temperature	X	X	X	X	X	X	X	X	X	X	X	X	X	X	X	X
Blood pressure/pulse rate	X	X	X	X	X	X	X	X	X	X	X	X	X	X	X	X
Physical examination	X	X	X	X	X	X	X	X	X	X	X	X	X	X	X	X
Electrocardiogram	X	X	X	X	X	X	X	X	X	X	X	X	X	X	X	X

Commercially Confidential Information

Hematology/Clinical Chemistry/ Urinanalysis ⁹	X	X	X	X	X	X	X	X	X	X	X	X	X	X	X	X
Hepatitis, CMV, HIV screen	X ²		X ⁸		X ⁸											
TB screen	X															
FSH ³	X															
Pregnancy test ³	X	X	X	X	X	X	X	X	X	X	X	X	X	X	X	X
ESR, CRP	X	X		X	X	X	X	X	X	X	X	X	X	X	X	X
IgG, IgM	X	X			X			X				X		X		X
C3, C4 Complement	X	X			X			X				X		X		X
Lupus anticoagulant	X		X								X					X
Coagulation test	X	X		X	X	X	X	X	X	X	X	X	X	X	X	X
PK collection ¹			X	X		X	X		X	X	X	X	X	X	X	X
PD collection (total soluble CD40)			X		X				X				X		X	X
Immunogenicity			X		X			X		X		X		X		X

Commercially Confidential Information

Drug administration		X	X	X	X	X	X	X	X							
Study completion																X

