8.6.8.2 Hepatitis, CMV, HIV screening

Hepatitis

All subjects will be screened for Hepatitis B surface antigen (HBsAg) and Hepatitis B core antibody (anti-HBc); HBV DNA testing will be performed if needed.

- If HBsAg is positive then the patient is **not eligible**, regardless of other test results, and HBV DNA test is not required.
- If HBsAg and anti-HBc are both negative, then the patient is **eligible** and HBV DNA test is not required.
- If HBsAg is negative and anti-HBc is positive then HBV DNA test has to be performed to confirm eligibility: the subject is only eligible if HBV DNA is negative.
 - For such subjects an expert in hepatitis must be consulted and recommendations followed. If enrolled, hepatitis B monitoring must be implemented: HBsAg and HBV DNA tested every 4 weeks until the end of study.

- In case of sero-conversion (i.e., if either HBsAg or HBV DNA turn positive) preemptive anti-viral treatment (e.g., lamivudine or entecavir) must be initiated immediately.

For subjects who are ineligible for the study based on hepatitis B screening, appropriate treatment should be considered.

Table 8-2 Hepatitis screening

HBsAg	Anti-HBc	HBV DNA	Eligible	Comment
-	-	not required	Yes	
-	+	-	Yes	Monitoring required
-	+	+	No	Consider treatment
+	+ or -	not required	No	Consider treatment

Screening for Hepatitis C will be based on HCV antibodies and HCV RNA.

CMV

Guidance to investigators:

CMV infections will be recorded as Adverse Events and on the CMV-specific CRF page. CMV infection is identified by assessments of laboratory and/or clinical sign/symptoms.

Cytomegalovirus disease is defined according to published criteria ([Ljungman et al 2017](#); [Choo et al 2019](#)) as described below.

- a. ACTIVE CYTOMEGALOVIRUS INFECTION is defined as a detectable cytomegalovirus viral load in the absence of signs or symptoms attributable to cytomegalovirus. Active cytomegalovirus infection can be the result of cytomegalovirus reactivation or primary cytomegalovirus infection.

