- b. PROVEN DISEASE: For pneumonia, central nervous system (CNS) disease, gastrointestinal disease, hepatitis, nephritis, cystitis, myocarditis, pancreatitis, and disease in other organs, definite tissue-invasive disease requires the correct clinical syndrome combined with the detection of cytomegalovirus in tissue samples (or in bronchoalveolar lavage fluid for pneumonia) by virus isolation, immunohistochemical analysis, in situ hybridization, or conventional histologic features. Detection of cytomegalovirus by PCR alone is not sufficient.
 - Cytomegalovirus viral syndrome requires fever (oral temperature $>38^{\circ}\text{C}$) for two or more days within a 4-day period, neutropenia or thrombocytopenia, and the detection of cytomegalovirus in the blood by culture or the detection of antigen, DNA, or RNA. Human herpes virus -6 (HHV-6) infection needs to be excluded.
 - For central nervous system (CNS) disease, detection of cytomegalovirus in cerebrospinal fluid (CSF) samples by culture or PCR is sufficient.
 - For retinitis, typical cytomegalovirus lesions must be confirmed by an ophthalmologist; detection of cytomegalovirus is not required.
- c. PROBABLE DISEASE requires the correct clinical syndrome but the detection of cytomegalovirus cannot be confirmed as outlined above.

Detection During Screening and monitoring:

1. At study screening, patients with active viral infections (quantifiable CMV DNA by PCR or positive IgM in the absence of a positive IgG) will not be eligible for randomization
2. All patients will be monitored for potential CMV reactivation or new primary infections by CMV (IgG and IgM) serology and viral DNA using PCR from randomization visit and monthly thereafter
3. In case of suspicion CMV infection, CMV serology will be performed as soon as possible, i.e. not waiting for the next scheduled CMV monitoring.
4. For patients currently ongoing in the study (i.e. patients enrolled under Protocol version 02 dated 22May2019 and continuing with study follow up period), CMV monitoring should be implemented at the next scheduled visit as per protocol

Table 8-3 CMV screening

IgM	IgG	DNA (PCR) detectable	DNA (PCR) quantifiable	Eligible	Comment
+	-			No	Regardless of DNA results: patient not eligible.
			+	No	Regardless of any other results: patient not eligible.
Examples of non-eligibility					
+	-	-	-	No	IgM positive and IgG negative: patient not eligible.
-	-	+	+	No	DNA quantifiable: patient not eligible

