9.3.2 SAE reporting

Screen Failures

Note the following requirement for Screen Failures: SAEs occurring after the subject has provided informed consent until the time the subject is deemed a Screen Failure must be reported to Novartis.

Randomized Subjects

To ensure subject safety, every SAE, regardless of causality, occurring after the subject has provided informed consent and until 30 days after the last study visit must be reported to Novartis within 24 hours of learning of its occurrence as described below.

Any SAEs experienced after this period should only be reported to Novartis if the investigator suspects a causal relationship to study treatment.

All follow-up information for the SAE including information on complications, progression of the initial SAE and recurrent episodes must be reported as follow-up to the original episode within 24 hours of the investigator receiving the follow-up information. An SAE occurring at a different time interval or otherwise considered completely unrelated to a previously reported one must be reported separately as a new event.

Follow-up information provided must describe whether the event has resolved or continues, if and how it was treated, whether the blind was broken or not (if applicable) and whether the subject continued or withdrew from study participation. Each re-occurrence, complication, or progression of the original event must be reported as a follow-up to that event regardless of when it occurs.

If the SAE is not previously documented in the Investigator's Brochure or Package Insert (new occurrence) and is thought to be related to the study treatment a Chief Medical Office and Patient Safety (CMO& PS) Department associate may urgently require further information from the investigator for Health Authority reporting. Novartis may need to issue an Investigator Notification (IN) to inform all investigators involved in any study with the same study treatment that this SAE has been reported. Suspected Unexpected Serious Adverse Reactions (SUSARs) will be collected and reported to the competent authorities and relevant ethics committees in accordance with EU Guidance 2011/C 172/01 or as per national regulatory requirements in participating countries.

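### Section 6.6 lets a consenting patient be taken out of the study after a dosing deviation, contrary to Sections 7.2 and 8.1, which can end safety follow-up while drug effect is still expected

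*Protocol*

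**What the plan says.** Protocol Section 6.6 does not permit dose adjustments or interruptions. If the dosing scheme is departed from, because of an AE or for any other reason (non-compliance and operational problems are the examples), site and sponsor must consult and agree "to decide whether the subject can continue or needs to be withdrawn from the study".

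Other sections treat stopping drug and leaving the study as different things:

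- Section 7.2: "Patients who discontinue study treatment are to continue their study participation, and to complete all study visits". It adds that even patients who no longer wish to take part do not count as withdrawn unless they withdraw consent.
- Section 7.3 confines withdrawal of consent to patients who want to leave and also refuse further data collection.
- Section 8.1: "Subjects who prematurely discontinue the study drug for any reason should be continuing their study participation, i.e., to complete all study visits".
- Section 6.7, on the comparable decision after an emergency code break, calls for an assessment only "to assess whether or not study treatment should be discontinued for a given subject".

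**The concern.** Section 6.6 is where a site will look after a missed or altered infusion, and its trigger is broad. Read literally, it lets a patient who has not withdrawn consent be removed from the study, which Section 7.2 does not allow even for a patient who has lost interest in taking part.

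The stake is safety follow-up, which serves a primary objective. Section 3.6.2.2 states that after stopping CFZ533 "insufficient humoral immune response is likely to persist until 14 weeks after the last dose". A patient withdrawn under Section 6.6 would lose the following in that period:

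- the scheduled safety visits;
- the CMV monitoring in Section 8.6.8.2 ("serology and viral DNA using PCR from randomization visit and monthly thereafter");
- for anti-HBc-positive patients, the hepatitis B monitoring ("HBsAg and HBV DNA tested every 4 weeks until the end of study");
- part of the all-causality SAE window in Section 9.3.2, which is tied to the last visit.

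The additional analyses regardless of adherence in SAP Section 6.1.1 would also lose data. The SAP does not make clear whether these depend on more than 15% of patients failing the steroid taper.

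**Working it through.** The plan gives no figure of its own on this point, so the check is day arithmetic for a single patient.

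**Inputs**
- Infusions on Days 1, 15, 29, 57, 85, 113 and 141 (Protocol summary).
- Later visits every 28 days from Day 169 to Day 337 (Table 8-1).
- Expected effect lasts 14 weeks = 98 days after the last dose (Section 3.6.2.2). Section 5.2 gives a washout of about 16 weeks = 112 days.
- All-causality SAE reporting covers SAEs "occurring after the subject has provided informed consent and until 30 days after the last study visit must be reported to Novartis" (Section 9.3.2).
- Assumption: the last study visit is the one at which the infusion was missed or, in the third case, the day of the last infusion.

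**Formulas**
- Effect ends = last dose day + 98.
- SAE window ends = last visit day + 30.
- Gap = effect end − window end.

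| Case | Last dose | Last visit | Effect ends | SAE window ends | Gap |
|---|---|---|---|---|---|
| Day 85 infusion missed, patient withdrawn | 57 | 85 | 57 + 98 = 155 | 85 + 30 = 115 | 40 days |
| Day 15 infusion missed, patient withdrawn | 1 | 15 | 1 + 98 = 99 | 15 + 30 = 45 | 54 days |
| Withdrawn on the day of a dose, d | d | d | d + 98 | d + 30 | 68 days |
| Drug stopped after Day 57, followed under 7.2 | 57 | 337 | 155 | 337 + 30 = 367 | none |
| All doses given | 141 | 337 | 141 + 98 = 239 | 367 | none |

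Using the 16-week washout adds 112 − 98 = 14 days to each gap: 54, 68 and 82 days.

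**Visits lost when withdrawn at Day 85:** Days 113, 141, 169, 197, 225, 253, 281, 309 and 337, nine in all. Two of them (Days 113 and 141) fall on or before Day 155. The SAE window is shortened by 367 − 115 = 252 days.

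**Primary analysis:** Protocol Section 11.4.3 and SAP Section 6.1.1 exclude UPCR data from the date of drug discontinuation. Keeping these patients in the study therefore leaves the primary Week 25 UPCR analysis unchanged.

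**The case against.** The strongest reply is that Sections 7.2 and 8.1 are the dedicated rules, that Section 6.6 only says who must be consulted, and that the sponsor whose agreement is required also wrote those rules. The word *continue* in Section 6.6 has no object and could mean continue in the study, on or off drug. That reading is possible, but it does not remove the other branch, which still ends study participation for a consenting patient.

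The 14 weeks may also be too long after a single dose. Section 1.3.2.1 reports that full CD40 occupancy was generally maintained for 8 weeks (56 days) at 10 mg/kg IV in rheumatoid arthritis. Used as the measure for the missed Day 15 case, this gives 1 + 56 = Day 57 against Day 45, a gap of 12 days. The point stands in part. Full occupancy is not the end of effect, but 12 to 54 days is a fair range for that case, and the 68-day figure would likewise fall for an exit on Day 1. The 40-day case follows four infusions (Days 1, 15, 29 and 57), so the single-dose evidence does not bear on it directly. Exit could also come later than the missed visit, since consultation comes first.

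Finally, some safety cover remains. SAEs suspected to be related are reportable after the window (Section 9.3.2), patients are told to report later events they believe related (Section 9.1), and unresolved AEs can receive extra visits (Section 7.2). None of these replaces scheduled viral testing or SAE capture regardless of causality.

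It is also true that withdrawal under Section 6.6 is permissive, and that Sections 6.11 and 8.6.7 use similar study-level wording. Both suggest loose terminology rather than a deliberate exit route.

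**Conclusion.** The concern holds. Section 6.6 is current, operative text and conflicts with Sections 7.2 and 8.1 as written. For a patient last dosed on Day 57 and withdrawn at Day 85, the cost is nine visits and 40 days of expected effect outside all-causality SAE reporting. Across the cases the gap is 40 to 68 days on the 14-week figure and 54 to 82 days on the 16-week washout. The single-dose cases may be shorter, down to 12 days for a missed Day 15 infusion. These figures assume exit at the visit of the missed or last infusion.

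The practical reach is probably modest, because withdrawal needs sponsor agreement. No trial-level loss can be given without a deviation rate. The correction is still worth making, because it protects follow-up for a primary objective at almost no cost.

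**What to change.** In Section 6.6, make the decision one about study treatment only. Suggested wording for the clause: *to decide whether the subject can continue study treatment or must discontinue it; subjects who discontinue study treatment remain in the study and complete all remaining visits per Section 7.2 unless they withdraw consent*. Leave the dosing decision, and the need for sponsor agreement to it, as they are. The similar phrases in Sections 6.11 and 8.6.7 could be aligned in the same amendment.

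The cost is one sentence in a protocol amendment. The visits and tests are already in the assessment schedule, and neither the sample size nor the primary analysis changes.

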6.7 Emergency breaking of assigned treatment code

Emergency code breaks must only be undertaken when it is required to in order to treat the subject safely. Most often, study treatment discontinuation and knowledge of the possible treatment assignments are sufficient to treat a study subject who presents with an emergency condition. Emergency treatment code breaks are performed using the IRT. When the investigator contacts the system to break a treatment code for a subject, he/she must provide the

requested subject identifying information and confirm the necessity to break the treatment code for the subject. The investigator will then receive details of the investigational drug treatment for the specified subject and a fax or email confirming this information. The system will automatically inform the study monitor for the site and the Study Team that the code has been broken.

It is the investigator's responsibility to ensure that there is a dependable procedure in place to allow access to the IRT cards at any time in case of emergency. The investigator will need to provide:

- protocol number
- study drug name
- subject number.

In addition, the investigator must provide oral and written information to inform the subject how to contact his/her backup in cases of emergency when he/she is unavailable to ensure that un-blinding can be performed at any time.

An assessment will be done by the appropriate site personnel and sponsor after an emergency unblinding to assess whether or not study treatment should be discontinued for a given subject.

